9.2 Reported Side Effects

The incidence of reported side effects from the subject diary will be summarized by week (from dosing) and treatment group.

First, an overall Fisher's Exact test will be carried out to compare each safety parameter among all four treatment groups. If this overall test is significant ($p\text{-value} \leq 0.05$), pairwise comparisons will be carried out to compare the 3M Oral Rinse and the vehicle control. Each active vs vehicle comparison will be carried out at an alpha level of 0.05.

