9.1 Adverse Events

All adverse events (AEs) occurring after initiation of study treatment (treatment emergent AEs) will be summarized by severity, relatedness, overall and treatment group. AEs occurring during the screening period will be summarized separately. All AEs will be classified using the MedDRA dictionary.

All verbatim descriptions will be listed for all AEs, along with information regarding onset, duration, severity, relationship to treatment, and action taken.

Serious adverse events will be summarized and presented according to nature, time to onset, duration, relationship to treatment and outcome.

First, an overall Fisher's Exact test will be carried out to compare each safety parameter among all four treatment groups. If this overall test is significant ($p\text{-value} \leq 0.05$), pairwise comparisons will be carried out to compare the 3M Oral Rinse and the vehicle control. Each active vs vehicle comparison will be carried out at an alpha level of 0.05.

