4.4 Risk/Benefit Summary

4.4.1 Risks and Benefits of the Experimental Device and Clinical Investigation

The anticipated clinical benefit of the 3M Oral Rinse and the predicate oral rinse is control of plaque and gingivitis. Subjects who receive placebos may not receive the same benefit as those who receive active treatment.

Subjects will be instructed to refrain from any dental treatment, including dental prophylaxis, during the study. If necessary, emergency dental treatment may be performed. Subjects will be instructed to inform the investigator as soon as possible if any emergency dental treatment is performed. The investigator will then decide whether the subject should continue in the study. Subjects who receive medical and/or dental treatment with antibiotic management may be dropped from the study.

The following is a list of potential risks associated with this study.

- Plaque and gingivitis may not improve
- Subjects may have an increased risk of disease or infection from altered oral mucosal immunity due to potential changes in oral flora
- Potential allergies to product components
- Oral rinses can cause transient mouth/tongue numbness
- Oral rinses can cause mucosal sloughing/irritation
- Oral rinses can cause transient dry mouth
- Oral rinses may cause transient alteration in taste
- Subjects may experience bleeding gums during study visits with clinicians due to probing/gingivitis assessment procedures
- Subjects should avoid rinse contact with skin and eyes. In case of contact with skin, wash thoroughly and in case of contact with eyes, flush with water.

5. Study Design and Study Objectives/Endpoints

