5.1 Study Design

This is a prospective, single site, randomized, parallel, blinded clinical trial. Subjects will be randomly assigned to one of four treatment groups identified as Product A, Product B, Product C or Product D.

Subjects will be screened for eligibility and entered into a washout period that is at least 7 days, during which time they will be provided with study toothbrush, toothpaste and dental floss. No oral rinses or medication that alters oral tissue health will be used or taken during the washout period. After randomization, the designated rinse will be placed into a non-transparent container so that other subjects and clinical examiners do not see the allocated rinse per the randomization schedule.

Subjects will be provided with both verbal and written instructions to take home, and a diary for tracking dosing compliance and any side effects from rinse use. Subjects will return the diary along with the empty/used/unused rinse bottles in the original container at their next scheduled visit to monitor for compliance of product use. Subjects that are found to be non-compliant will remain in the study, be re-trained and documented accordingly.

Examinations for the clinical endpoints (PI, GI and BI) will be conducted at the baseline, 3-month (± 10 days), and 6-month (± 10 days) visits.

Interim visits will be scheduled to review diary, replenish study supplies, check study compliance, etc. Subjects will be provided Colgate Regular toothpaste, dental floss and a soft toothbrush (replaced at 3 months) for use during the 6-month study period.

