9. ASSESSMENT OF SAFETY

9.1 Safety Parameters

The principal measure of safety will be the incidence of adverse events reported during the study.

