9.3 Adverse Events

An adverse event (AE) can be identified via visual examination by the dental examiner or reported by the subject. The Investigator is responsible for identifying AEs throughout the study. An AE may occur at any time during the conduct of the study, in any phase of the study or after the study is completed.

Examples of AEs that are considered expected during the conduct of the study include the following: mucosal sloughing, taste alteration, mouth or tongue numbness or tingling, and dry mouth. In addition, irritated or bleeding gums may occur due to probing during the dental examination.

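### SAP 9.2 summarises diary side effects only by week and leaves its Fisher test parameter undefined; no count of subjects affected at any time on treatment is planned

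*SAP*

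**What the plan says.** Subjects keep "a diary for tracking dosing compliance and any side effects from rinse use" (protocol 5.1). Reported side effects belong to the safety objective (SAP 2.2, protocol 5.5) and are listed separately from adverse events among the safety variables (SAP 9, protocol 11.6).

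SAP 9.2 gives one summary of the diary data: "The incidence of reported side effects from the subject diary will be summarized by week (from dosing) and treatment group". It continues: "First, an overall Fisher's Exact test will be carried out to compare each safety parameter among all four treatment groups". If that test is significant at 0.05, 3M Oral Rinse is compared with vehicle: "Each active vs vehicle comparison will be carried out at an alpha level of 0.05". Neither SAP 9.2 nor protocol 11.6 says whether the parameter is incidence in a given week or incidence at any time on treatment.

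Protocol 4.4.1 lists potential risks of rinses in general, for example "Oral rinses can cause transient mouth/tongue numbness"; dry mouth and taste change are also called transient there. Protocol 9.3 gives as expected adverse events "mucosal sloughing, taste alteration, mouth or tongue numbness or tingling, and dry mouth". Treatment-emergent adverse events "will be summarized by severity, relatedness, overall and treatment group" (SAP 9.1), and they are coded in MedDRA. Protocol 9.1 states: "The principal measure of safety will be the incidence of adverse events reported during the study".

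**The concern.** The question a reader brings to a side-effect table is how many subjects on each rinse had the effect at least once. A by-week table does not answer it. Subjects affected in different weeks are never added together, and the weekly percentages cannot be summed afterwards without knowing who recurs.

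Dosing lasts six months, about 26 weekly intervals. If subjects on 3M Oral Rinse are affected at different times, an excess that is large over the whole period can appear as a run of small weekly differences and be read as no difference.

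The undefined test parameter adds to this. If the test is run by week, there are about 26 gated tests per type of effect. If it is run on any-time incidence, the SAP never defines that variable. Either way the choice is left to the analyst.

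**Working it through.** **Planned summaries side by side.** SAP 9.2 (diary) gives by-week incidence and nothing over the whole period. SAP 9.1 (adverse events) covers the whole treatment period, broken down by severity, relatedness and arm, with MedDRA coding and a listing, but names no table by type of event. SAP 9.3 (oral tissue) gives a by-visit table plus two summaries across visits: worst finding up to 3 months, and baseline to last visit. So a cross-visit summary was thought necessary for tissue findings, and 9.2 has no counterpart.

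**The plan's own figure.** The documents give no side-effect rate and no power for safety. The only sizing is for GI and PI: 34 per group for a difference of 0.40, SD 0.5, one-sided 0.025, 90% power. It reproduces (t-based power 90.2% at 34, 89.3% at 33) and is not at issue. What matters here is the planned 50 per arm (protocol 11.8).

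**What one week needs.** Suppose k subjects are affected on 3M Oral Rinse and none elsewhere, with 50 per arm. Sidedness is not stated for the follow-on test; two-sided is assumed.

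- Four-arm Fisher: p = 4·C(50,k)/C(200,k)
- 3M versus vehicle Fisher: p = 2·C(50,k)/C(100,k)

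| k versus 0 | Four-arm p | 3M versus vehicle p |
|---|---|---|
| 3 | 0.060 | 0.242 |
| 4 | 0.014 | 0.117 |
| 5 | 0.003 | 0.056 |
| 6 | 0.0008 | 0.027 |

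The pairwise step binds: six subjects in the same week, with none on vehicle.

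**One worked split.** Take 20 of 50 on 3M Oral Rinse and 5 of 50 in each other arm, at any time. The four-arm p is 0.0001 and the pairwise p is 0.001. Spread evenly over 26 weeks, this is 20/26 = 0.77 subjects per week against 5/26 = 0.19, so no single week would be expected to come near six.

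**Simulation.** There were 1,500 trials per scenario, with 50 per arm, complete diaries and one one-week episode per affected subject. Onset was uniform over the stated number of weeks. A flag means that the four-arm test and then 3M versus vehicle are both at or below 0.05. The rule was applied once to any-time incidence, and separately to each of 26 weekly tables. All rates are assumptions.

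| 3M versus each other arm | Any-time flag | Weekly flag: onset over 1 week | 4 weeks | 12 weeks | 26 weeks |
|---|---|---|---|---|---|
| 30% versus 10% | about 61% | 60% | 23% | 1.5% | 0% |
| 40% versus 10% | about 92% | 92% | 52% | 4% | 0.2% |
| 50% versus 20% | about 84% | 85% | 43% | 10% | 1% |

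Simulation error is small: at 52% the standard error is √(0.52 × 0.48/1,500) = 1.3 points.

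A separate check at 30% versus 5%, using only the pairwise step, gives the same pattern: any-time 89–90%; weekly 90%, 37%, 1% and 0.1% for onset over 1, 4, 13 and 26 weeks. The any-time result does not depend on timing. The weekly result depends on it almost entirely.

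**The case against.** The case on the other side is substantial and narrows the point in four ways.

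- **A reader might infer that the share of subjects affected is never reported.** That goes too far. Protocol 9.3 lists the same effects as expected adverse events and accepts subject reports. Protocol 9.3.2 has the site record every adverse event, related or not, and diaries are reviewed at each post-baseline scheduled visit. SAP 9.1 then summarises events by arm over the whole period with MedDRA coding, and adverse event incidence is the principal safety measure. An any-time figure may therefore emerge there. However, the documents never say that diary entries are recorded as adverse events, and 9.1 does not name a table by type of effect.
- **A reader might take the Fisher test to be weekly.** The text does not say so. The same sentence stands in SAP 9.1, where nothing is weekly, and one test per side effect is a natural reading. The defect is an undefined parameter.
- **A reader might blame short duration.** Duration alone hides nothing. If onsets cluster in one week, as they might with a rinse used from the first day, weekly and any-time tables do equally well (92% each at 40% versus 10%). An effect that recurs after each rinse would also show up weekly. The loss comes from staggered onset.
- **A reader might expect dropout to flatter the arm with the harm.** SAP 9.2 states no weekly denominator, so this is possible, but nothing here quantifies it, and SAP 7.1 reports reasons for discontinuation by arm.

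Protocol 4.4.1 also does not call mucosal sloughing transient, and its list concerns rinses in general rather than established harms of this product.

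**Conclusion.** The point holds in a limited form. SAP 9.2 specifies a measure that does not count affected subjects over the treatment period, and it leaves the parameter for its own test undefined. Whether SAP 9.1 fills the gap depends on a link between diary and adverse event records that the documents leave open.

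The size depends on timing. At an assumed 40% versus 10%, relying on weekly tables costs nothing if onsets fall in one week. It costs about 40 percentage points of detection (92% to 52%) if they spread over four weeks, and nearly all detection over 12 weeks or more. These figures assume 50 per arm with full diaries, single one-week episodes and a two-sided test. Longer episodes would lose less. No efficacy result and not the principal safety measure is touched. The change is worth making because the side-effect objective is explicit and the better measure comes from data already collected.

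**What to change.** In SAP 9.2:

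1. Make the main summary the number and percentage of subjects per arm who reported each type of side effect at least once during treatment, with the 3M-minus-vehicle difference and its 95% CI. For the 20/50 versus 5/50 split above, the difference is 30 points with SE √(0.4 × 0.6/50 + 0.1 × 0.9/50) = 0.081, so a simple interval of roughly 14 to 46 points.
2. Name this any-time incidence as the parameter for the four-arm Fisher test and the follow-on comparison with vehicle.
3. Keep the by-week table as a descriptive display of timing, and show the number of subjects with diary data in each week.
4. State how diary entries map to adverse events, so that the tables from SAP 9.1 and 9.2 can be read together.

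The cost is a few lines of text and one extra table, with no new data or visits. The any-time figure does not show duration; the retained weekly table does.

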9.3 Soft and Hard Oral Tissue Assessment

The incidence of normal and abnormal soft and hard tissue findings will be summarized by visit and treatment group. Shifts in findings from normal/abnormal to normal/abnormal observed within the first 3 months will be summarized by treatment group. The worst assessment up to the 3-month visit will be used in this summary. In addition, shifts in findings from normal/abnormal to normal/abnormal between the baseline visit and the last available visit will be summarized by treatment group.

Revision History

Revision Details:

- 1 To establish statistical analysis plan before study enrollment.
- 2
 - (1) To clarify when per protocol dataset will be applied (Section 5.3).
 - (2) To clarify dosing compliance computation (Section 7.4)
 - (3) To indicate the classification of AEs using the MedDRA dictionary (Section 9.1)
 - (4) To clarify the incorporation of the unscheduled oral assessment data in planned summaries (Section 9.3).

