11.6 Safety Analysis

Safety variables will include adverse events, abnormal soft and hard oral tissue, and reported side effects. First, an overall test will be carried out to compare each safety parameter among all four treatment groups. If this overall test is significant ($p\text{-value} \leq 0.05$), pairwise comparisons will be carried out to compare the 3M Oral Rinse and the vehicle control. Each active vs vehicle comparison will be carried out at an alpha level of 0.05.

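### SAP 9.3 omits the between-arm test of oral tissue findings that Protocol 11.6 calls for, and its shift tables miss an abnormality seen off-schedule after month 3 that clears by the last visit

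*SAP*

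**What the plan says.** **Protocol 11.6 (Safety Analysis)** names the variables: "Safety variables will include adverse events, abnormal soft and hard oral tissue, and reported side effects". It then sets a two-step comparison: "First, an overall test will be carried out to compare each safety parameter among all four treatment groups". If that p-value is at most 0.05, "pairwise comparisons will be carried out to compare the 3M Oral Rinse and the vehicle control", and "Each active vs vehicle comparison will be carried out at an alpha level of 0.05". The section does not name the type of test.

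**SAP 9 to 9.3.** Section 9 lists the same three variables. Section 9.1, on adverse events, makes the protocol's step specific: "First, an overall Fisher's Exact test will be carried out to compare each safety parameter among all four treatment groups". The same conditional follow-up comes after it. Section 9.2 repeats that paragraph for diary-reported side effects. Section 9.3, on oral tissue, opens with "The incidence of normal and abnormal soft and hard tissue findings will be summarized by visit and treatment group" and adds two shift summaries. For the summary covering the first three months, "The worst assessment up to the 3-month visit will be used in this summary". In the other, shifts "between the baseline visit and the last available visit will be summarized by treatment group". Section 9.3 mentions no test.

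**When tissue is examined.** The study schedule in the protocol synopsis places the oral exam at baseline, month 3, month 6 and any unscheduled visit. Protocol 8.1.5 lists no oral exam at the 4.5-month visit. Protocol 9.2 allows an unscheduled visit at any time.

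**The concern.** There are two separate defects in one section.

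First, the SAP is meant to add detail to the protocol's analyses. For one of the protocol's three safety variables it gives less. Tissue change is also the item named first in the safety objective (Protocol 5.5, SAP 2.2). If no test is planned, any comparison reported later would rest on choices made after the fact: which visit, worst or last finding, soft and hard tissue pooled or separate.

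Second, the rule that catches transient findings operates only in the first half of treatment. Before month 3, an abnormality that appears and resolves is kept by the worst-assessment rule. After month 3, the same event can drop out of both shift tables. The protocol expects effects of this kind: Protocol 9.3 gives mucosal sloughing as an expected event, and Protocol 4.4.1 describes several rinse effects as transient.

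**Working it through.** The plan gives no rate or calculation for tissue findings, so there is no figure to reproduce. The 34 per group in SAP 6.1 concerns PI and GI only.

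**1. Where the test is written**

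| Safety variable | Protocol 11.6 | SAP |
|---|---|---|
| Adverse events | overall four-arm test, then 3M vs vehicle if p ≤ 0.05 | 9.1: Fisher's exact, same two steps |
| Reported side effects | same | 9.2: same paragraph repeated |
| Abnormal oral tissue | same | 9.3: tabulations by arm, no test |

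**2. Which late abnormalities the shift tables keep**

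I read both tables as starting from baseline. Take a subject who is normal (N) at baseline and has an abnormal finding (A) after month 3 but before the last visit. Two things can still vary: the worst finding up to month 3 and the finding at the last visit. That gives 2 × 2 = 4 paths.

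| Worst to month 3 | After month 3 | Last visit | Table to month 3 | Table to last visit | Kept? |
|---|---|---|---|---|---|
| N | A | N | N→N | N→N | no |
| N | A | A | N→N | N→A | yes |
| A | A | N | N→A | N→N | yes |
| A | A | A | N→A | N→A | yes |

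One path is lost. Because no oral exam is scheduled between months 3 and 6, it needs an unscheduled exam. For a completer without one, month 6 is the only exam after month 3, so the last finding is also the worst in that period and nothing is missed. A table of baseline against worst finding through month 6 would classify the lost path as N→A.

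**3. What the omitted test could detect (illustration only)**

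Assumptions, none of them from the documents: 50 assessed subjects per arm, all normal at baseline; 5% with a new abnormality in each of the other three arms; two-sided 0.05 at both steps. The results come from 2,000 simulated trials per row.

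| Rate on 3M Oral Rinse | Overall test significant | Overall and 3M vs vehicle both significant |
|---|---|---|
| 10% | about 13% | about 5% |
| 20% | about 70% | about 49% |
| 30% | about 97% | about 89% |

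For scale, consider zero events on vehicle and k on 3M Oral Rinse, with 50 per arm. The pairwise Fisher p-value is 2·C(50,k)/C(100,k). This gives 0.056 for k = 5 and 0.027 for k = 6, so at least six events against none are needed. The test would therefore pick up a large excess and often miss a modest one.

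The number at risk may also be below 50. Entry requires a GI of at least 1.0, and Protocol 8.2.3.1 counts inflamed gingiva among its examples of abnormal soft tissue, so some subjects may already be abnormal at baseline.

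**The case against.** The best defence of the SAP is textual. Section 9 lists tissue findings as a safety variable, the paragraphs in 9.1 and 9.2 refer to every safety parameter, and nothing in 9.3 withdraws the protocol's test. On that reading the test is already planned and a paragraph simply was not repeated. This stands in part: a reader might infer that the sponsor decided to drop the test, and the documents do not show that. But if one statement were meant to cover everything, 9.2 would not need its own copy. Even on the generous reading, the tissue outcome to be tested is never defined.

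On the shift tables, the defence is that little can be lost. The gap needs an unscheduled exam after month 3, a finding that has cleared by the last visit, and no abnormality up to month 3. Under Protocol 9.3 the examiner can record a visible finding as an adverse event. Adverse events are compared between arms, and Protocol 9.1 makes their incidence the principal safety measure. The late finding might also appear in the by-visit incidence, although 9.3 does not say whether unscheduled visits are shown there. All of this stands and limits the consequence. It does not make the shift tables correct, since a new abnormality is still shown as no change.

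**Conclusion.** Both defects hold, within limits. The between-arm comparison that Protocol 11.6 sets for tissue findings is absent from SAP 9.3 or at best ambiguous, and no reason is given for a departure. One of four late-abnormality paths is misclassified in both shift tables. Its frequency cannot be estimated from the documents. The effect is confined to safety reporting; neither the primary comparison nor the success criterion is touched.

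Three stronger conclusions that a reader might draw are not supported:

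- *That tissue findings have no by-arm information at all.* Incidence and shifts are tabulated by arm. What is missing is the planned test.
- *That half of the six-month exposure is unobserved.* Only findings at unscheduled exams after month 3 are exposed to the gap.
- *That Protocol 11.6 requires a risk difference, a confidence interval, Fisher's test or separate soft and hard analyses.* It requires none of these. It requires the four-arm test before the pairwise one.

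The conclusion assumes that both shift tables start from baseline and that unscheduled oral exams feed section 9.3, as the SAP revision history indicates. The power figures above are illustrative, and the verdict does not depend on them.

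**What to change.** Amend SAP 9.3 before unblinding:

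1. Add a shift summary by arm of baseline against the worst post-baseline assessment through month 6, taking scheduled and unscheduled exams together.
2. Add the two-step test already used in 9.1 and 9.2: an overall four-arm Fisher's exact test and, if p ≤ 0.05, 3M Oral Rinse against vehicle at 0.05. Define the outcome as the proportion of subjects normal at baseline who have any abnormal finding afterwards, and report the number at risk in each arm. Alternatively, state that no test will be done and justify the departure from Protocol 11.6.

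A risk difference with a 95% confidence interval, and separate results for soft and hard tissue, would help given the test's limited power. They are optional and go beyond what the protocol asks.

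The cost is one paragraph, one more table and one more safety test, all from data already collected.
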